Study Protocol and Statistical Analysis Plan for Research Project: "Design and Development of a Mobile App to Improve Adherence to Pre-exposure Prophylaxis in Men Who Have Sex with Men?" clinicaltrials.gov
#NCT04248790 December, 28, 2020

Study design: This study is an open label, single group assignment, interventional study, aiming to examine the preliminary effectiveness of the app in monitoring adherence to PrEP. The study expects to enroll participants since May, 2020 and follow-up for 4 months.

Participants:

Inclusion criteria:

- Male.
- Aged 20 or above.
- Resides in Taiwan and able to understand, read, and speak Mandarin Chinese.
- Remains HIV negative prior to and during the study period.
- The results of the laboratory tests are eligible to initiate PrEP.
- Currently taking PrEP or willing to initiate PrEP.
- Reports having 4 times or above anal sex with men in the past month.
- Owns an Android or Apple operating system (iOS) smartphone and willing to download the study app.
- Willing to wear the device we provided during the study period.

Exclusion criteria:

- With abnormal kidney function (creatinine clearance rate \leq 60 mL/minute).
- Currently on medication that might interact with PrEP, such as drugs contain lamivudine in the pre-PrEP assessment.

Sample size: above 30 participants and 70 participants at maximum. The sample size calculation is based on central limit theorem (CLT), which states that the distribution of sample means approximates a normal distribution as the sample size gets larger. CLT refers to that sample sizes equal to or greater than 30 are considered sufficient for the CLT to hold.

Interventions: The UPrEPU app is a self-monitoring tool to improve PrEP adherence regardless of the MSM user's choice of dosing regimen and lifestyle. All of participants will receive access to all the app capabilities. The app features include information on HIV testing locations, sex and PrEP diary and reminder of taking PrEP.

Data Collection:

Recruitment: Participants from two medical centers in two major cities of Taiwan. Potential study participants will be referred by physicians and case navigators from the clinics.

Screening: Their eligibility will be assessed by a screening tool available online. Screening questionnaire shown in Table 1. The participants' answers have to meet "Answers to enroll" in each question to enroll this study.

Table 1. Screening questionnaire

Questions	Options	Answers to enroll
What is your gender	 Male  Female	Male
Are you able to understand, read, and speak Mandarin Chinese	 Yes  No	Yes
Are you living in Taiwan	 Yes  No	Yes
HIV status	 Positive  Negative	Negative
Do you assess the pre-PrEP assessment and eligible to use PrEP	 Yes  No	Yes
Birth Year	Open question	<=1999
Currently or willing to use PrEP	 Yes  No	Yes
Do you ever have anal intercourse with men	 Yes  No	Yes
How many episodes of anal intercourse with men in the past month	Open question	>=4
What is your cell phone brands and models	Open question	Only smart phone is available

Afterward, trained research assistants will inform those who are eligible about the purposes of the study and the information that will be collected in the study.

Individuals who express interest in this study will be required to provide signed informed consent. For those who do not consent to participate, the reasons for declining participation will be documented.

Baseline visit: Eligible participants will download the UPrEPU app on their phone and answer a baseline questionnaire in the app regarding sociodemographics, mental health scales, sexual behaviors, and PrEP use at the baseline visit at the study site.

Participants will also receive a wearable device that collects physiological sensor data. Participants will be encouraged to use all app components over the next four months and wear the wearable devices at all times.

Follow-up visit: Participants will be followed up monthly for the four months at the two medical centers where they were recruited. Each monthly visit will include rapid testing for HIV antigen and antibodies, measuring TDF/FTC concentration, and complete a follow-up questionnaire on their mental health scales, sexual behaviors, and PrEP use. Depression and anxiety will be assessed by Patient Health

Questionnaire-9 (PHQ-9) and General Anxiety Disorder-7 (GAD-7). We collect these two mental health indicators since studies have shown that mental health status may be associated with adherence to medications.

Kidney function and sexually transmitted infections will be assessed at the end of follow-up. The system usability scale (SUS) for the UPrEPU app will be assessed during the first follow-up visit and at the end of the study. A face-to-face, semi-structured qualitative interview will be conducted at each visit to assess the feasibility of the app. It will focus on any technical challenges participants may have encountered, recommendations for app improvement, and their satisfaction and comfort in using this app. All interviews will take around 30 minutes and will be audio-recorded for transcription and analysis. Data collection Items and Schedule shown in Table 2.

Table 2. Data collection Items and Schedule

	Screening	Baseline	F-up -1	F-up -2	F-up -3	F-up -4
1. Eligibility/Interest	●					
2. Informed Consent	●					
3. Blood sample		●	●	●	●	●
A. Drug concentration ◎Can be collected either F-up-2, F-up-3, or F-up-4				◎	◎	◎
B. HIV test		●	●	●	●	●
C. Liver and kidney function		●				●
D. Syphilis screening		●				●
4. Installing UPrEPU app		●				
5. Set up smart device		●				
6. Receive data in smart device			●	●	●	●
7. Baseline questionnaire		●				

8. Follow-up questionnaire			●	●	●	●
9. SUS questionnaire			●			
10. APP feasibility interview			●	●	●	●
11. Incentive			\$20	\$20	\$20	\$20 OR \$53

Incentives: Participants will receive incentives for completing each follow-up visit and in-depth interview. This includes US \$20 cash for each follow-up visit and US \$33 cash for twice completing the in-depth interviews. Participants whose cumulative frequency of log-in and use of features reached 90% will receive an additional US \$33 at the end of the study.

Statistical analysis plan: Usability of the app will be measured by the System Usability Scale (SUS), a 10-item, 5-point Likert scale, which gives a global view of subjective assessment of usability [1]. A score above 50 out of 100 indicates acceptable [2]. The primary feasibility outcomes include frequency of app log-in, use of app components such as PrEP-taking and sexual behavior reports, and the length of time of the app use based on the app analytics. Descriptive statistics will be used and confidence intervals will be calculated to evaluate the primary feasibility outcomes. Secondary feasibility outcomes of this app will be analyzing data from qualitative interviews focusing on technical challenges and satisfaction of the app during the follow-up with thematic analysis methods.

We will examine the app users' effectiveness of adherence monitoring for this app by comparing the pill-taking reports in the PrEP-taking diary component in the app with the Tenofovir (TDF) and Emtricitabine (FTC) drug concentration in dried blood spot (DBS) samples in the previous seven days before the follow-up day. We will use correlation analysis to examine the consistency between the drug concentration in the DBS samples and self-reported PrEP diary in the app. Higher correlation reflects higher effectiveness of adherence monitoring.

Reference

1. Brooke J, *SUS-A quick and dirty usability scale*. Usability evaluation in industry. Vol. 189. 1996. 4-7.

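### The SUS cut-off for an acceptable app (above 50 of 100) is the all-neutral score, so ratings only marginally better than indifference earn the label

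*Combined protocol and SAP*

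**What the plan says.** The Statistical analysis plan section introduces the instrument: "Usability of the app will be measured by the System Usability Scale (SUS), a 10-item, 5-point Likert scale". It then gives one rule for reading the result, by citation: "A score above 50 out of 100 indicates acceptable [2". It does not give the item scoring. It does not say whether the rule applies to each participant, the mean or the median, and it ties no confidence interval to the SUS. The one sentence on intervals concerns other measures: "Descriptive statistics will be used and confidence intervals will be calculated to evaluate the primary feasibility outcomes". Those measures are log-in frequency, use of the components and time spent in the app.

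On timing, the Follow-up visit text says the SUS "will be assessed during the first follow-up visit and at the end of the study", while Table 2 marks it only at the first follow-up. On size, the plan says "Sample size: above 30 participants and 70 participants at maximum". It supports this with a general argument ("The sample size calculation is based on central limit theorem (CLT") and gives no standard deviation, target difference or precision.

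**The concern.** A cut-off for acceptability should separate an app that users find good enough from one they have no view on. This one sits at the point of no view, and a score that clears it shows only that ratings lean to the favourable side.

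The position of the cut-off matters because nothing else in the plan does this job. It is the only numeric benchmark attached to any outcome. The primary feasibility outcomes have no threshold, the adherence analysis says only that a higher correlation is better, and the 90% usage figure under Incentives is a payment rule. The study has a single group, so there is no comparator to put the score in context. A report that the app reached acceptable usability would rest on this sentence alone.

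**Working it through.** The cut-off is cited and not derived, so there is no calculation in the plan to reproduce. The check is what a score of 50 means on the scale described.

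**Inputs from the documents.** 10 items; 5 response points (1 to 5, midpoint 3); maximum 100; rule strictly above 50; more than 30 and at most 70 participants.

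**Assumptions.** Linear scoring with a minimum of 0, since the plan gives only the maximum. Between-participant SD of 10, 15 or 20, since the plan gives none.

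**1. Score of an all-neutral respondent.**
- All items keyed in the same direction: raw sum 10 × 3 = 30, possible range 10 to 50, so (30 − 10)/(50 − 10) × 100 = **50.0**.
- Half the items reversed: 2.5 × [5 × (3 − 1) + 5 × (5 − 3)] = 2.5 × 20 = **50.0**.

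The direction of item wording makes no difference.

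**2. Lowest individual score that passes.** There are 40 steps in 100 points, so one step is worth 2.5. All-neutral is 20 steps. One item one step better is 21 × 2.5 = **52.5**, an average shift of 1/10 = 0.1 of a step per item.

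**3. A group whose true mean is exactly 50.** Simulated scores were rounded to 2.5 points and kept within 0 to 100, with 100,000 runs for each combination of n = 30, 31, 70 and SD = 10, 15, 20.

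| Rule applied to the mean | Probability of passing |
|---|---|
| Mean above 50, no confidence limit | 0.492 to 0.499 |
| Lower 95% limit above 50 | 0.024 to 0.026 |

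The first row is what symmetry predicts: one half, less a little for means of exactly 50.

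**4. What the confidence-limit rule asks of the observed mean.** The half-width of the 95% interval is t × SD/√n.

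| n | SD 10 | SD 15 | SD 20 |
|---|---|---|---|
| 31 | 3.67 | 5.50 | 7.34 |
| 70 | 2.38 | 3.58 | 4.77 |

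The observed mean would have to exceed about 52.4 (n = 70, SD 10) to 57.3 (n = 31, SD 20).

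**5. A small favourable shift.** Suppose the true mean is 55. This value is illustrative: 5/2.5 = 2 steps spread over ten items, or 0.2 of a step per item. With n = 31 and a normal approximation, the chance that the bare mean exceeds 50 is Φ(5/(SD/√31)):
- SD 20: Φ(5/3.59) = Φ(1.39) = 0.92
- SD 15: Φ(5/2.69) = Φ(1.86) = 0.97
- SD 10: Φ(5/1.80) = Φ(2.78), above 0.99

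**The case against.** A reader might infer that an app to which users are wholly indifferent would be declared acceptable. The documents do not support that. The rule is a strict inequality, so uniform neutrality scores 50.0 and does not pass. An app with a true mean of 50 passes only about half the time, and only if the bare mean is what is compared. The sentence is also an interpretive label: SUS is in neither the primary nor the secondary feasibility list, and no hypothesis or go/no-go rule hangs on it.

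A reader might also infer that the rule can hardly fail, because participants are paid volunteers using an open-label app. No figure in the documents shows how far ratings would be raised. Payments are for visits, interviews and usage, not for ratings, and an app rated below neutral would tend to fail. Step 5 shows that a small shift would be enough, not that one will occur.

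The cut-off is attributed to an empirical evaluation of the SUS, and a midpoint can also be an empirically supported lower bound. Whether reference [2] supports 50 cannot be settled here. For the same reason no replacement value, such as 70, can be derived from these documents; on the plan's scale 70 would mean eight items one step above neutral, or 0.8 of a step per item.

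Finally, the plan is dated 28 December 2020, enrolment was expected from May 2020 and the SUS is first given at the first monthly visit. SUS data may already exist, so a new criterion could be post hoc.

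These points limit the claim and lower its severity. They do not touch the scoring arithmetic or supply the missing summary measure and visit.

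**Conclusion.** The point holds in this form: the plan's cut-off coincides with the score of a respondent who is neutral throughout, so the label goes to anything marginally better than neutral. The equality with 50 rests only on linear scoring from 0 to 100. The passing probability of about one half for a neutral app also assumes that the bare mean is compared with 50, which the plan leaves open; it barely changes over n = 30 to 70 and SD 10 to 20.

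Severity is moderate. The sentence governs how usability may be described, and a mean slightly above 50 should be described as better than neutral. It does not affect the primary feasibility outcomes or the adherence analysis.

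**What to change.** In the Statistical analysis plan section, replace the cut-off sentence with wording to this effect:

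> A SUS score of 50 is the neutral midpoint of the scale. Ratings will be described as better than neutral only if the lower 95% confidence limit of the mean SUS exceeds 50. Usability will be described as acceptable only if the criterion of [value, with its basis in reference 2] is met. The mean SUS with its 95% confidence interval and the share of participants at or above the criterion will be reported for [named assessment].

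The sponsor should:
- check the acceptability band in reference [2] and take from it a criterion clearly above 50. If the source offers none, the report should say better than neutral and not use the word acceptable;
- state whether the mean or its lower confidence limit must reach the criterion. The confidence limit is the consistent choice, because a bare mean compared with any value passes about half the time when the true mean equals that value;
- name the assessment used, and reconcile the text (two assessments) with Table 2 (one);
- disclose the change as post hoc if any SUS data have been seen, and in that case also report the result against the above-50 rule.

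The cost is a few sentences of SAP wording and no new data. The downside is that the app may no longer earn the label acceptable.

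### Do the app-use outcomes and the 90% bonus rule need a stated denominator, given that dosing regimen is the user's choice?

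*Combined protocol and SAP*

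**What the plan says.** The Statistical analysis plan section defines the outcomes in one sentence: "The primary feasibility outcomes include frequency of app log-in, use of app components such as PrEP-taking and sexual behavior reports", followed by "the length of time of the app use based on the app analytics". Their analysis is also one sentence: "Descriptive statistics will be used and confidence intervals will be calculated to evaluate the primary feasibility outcomes". Neither sentence gives a unit, an expected number of log-ins or reports, or a breakdown by regimen.

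The Incentives section contains the only percentage of use in the document: "Participants whose cumulative frequency of log-in and use of features reached 90% will receive an additional US" $33, paid when the study ends. It does not say what the 90% is a percentage of, or how log-in and feature use combine into one figure.

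Three other places bear on the point:

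- Interventions: the app is meant to work whatever the user's "choice of dosing regimen and lifestyle".
- Inclusion criteria: "Reports having 4 times or above anal sex with men in the past month". This is a floor with no ceiling.
- Study design and Baseline visit: the trial is an "open label, single group assignment, interventional study", and "Participants will be encouraged to use all app components over the next four months".

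**The concern.** A truthful PrEP-taking entry needs a dose, and a truthful sex entry needs an episode. Men on different regimens, or with different levels of sexual activity, can therefore report everything and still have very different counts. If component use were summarised as a pooled count, its mean would move with the share of non-daily users even when nobody missed a report. A reader could take a lower mean as poorer engagement. A share of expected reports would not have this property, so the choice of definition affects what a primary feasibility result means.

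The bonus adds a second worry. Log-in and feature use are two of the three primary feasibility outcomes and are also what the bonus pays for. With one group and no unpaid comparison, the trial cannot separate willing use from paid use. The 90% rule also cannot be reproduced from the text.

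**Working it through.** **Plan's own figure.** There is none to reproduce. The document gives no expected count, rate or target for app use, and the 90% has no base.

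**Inputs from the document.** Follow-up of four months; at least 4 episodes in the month before entry; regimen chosen by the user; a 90% rule.

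**Assumptions, not in the document.** 122 days; one report a day for a daily user; 1 to 4 reports per episode for a non-daily user; the entry rate of sexual activity continues; every report is made. These serve only to size the effect and describe no actual regimen.

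**Step 1: two perfect reporters.** Reports from a non-daily man = episodes per month × 4 months × reports per episode.

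- At 4 episodes a month: 4 × 4 × 1 = 16 to 4 × 4 × 4 = 64. Ratio to a daily user: 122/16 = 7.6 down to 122/64 = 1.9.
- At 8 episodes a month: 8 × 4 × 1 = 32 to 8 × 4 × 4 = 128, capped at one per day, so 122. Ratio: 122/32 = 3.8 down to 122/122 = 1.0.

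**Step 2: pooled mean.** Mean = 122(1 − p) + c·p, where p is the share of non-daily men and c their count.

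| p | c = 16 | c = 64 | c = 122 |
|---|---|---|---|
| 0 | 122 | 122 | 122 |
| 0.25 | 95.5 | 107.5 | 122 |
| 0.50 | 69 | 93 | 122 |
| 0.75 | 42.5 | 78.5 | 122 |

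At the entry floor, with p from 0.25 to 0.75, the mean is 42.5/122 = 35% to 107.5/122 = 88% of the all-daily value. With p = 0, or with more frequent activity and more reports per episode, it is 100%. The possible effect therefore runs from large to nil, and the document has nothing that narrows it.

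**Step 3: which outcomes are exposed.** The regimen argument concerns diary counts. Log-in does not require a dose or an episode, and days of follow-up are an obvious base for it. Length of use is already a quantity of time and needs no denominator. Both the four-month follow-up and the cumulative wording of the bonus rule point to a four-month window.

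**Step 4: the 90% rule.** The threshold depends on the base.

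- By day: 0.9 × 122 = 109.8, so 110 days.
- By episode at the entry floor: 0.9 × 16 = 14.4, so 15 episodes.

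A man with 16 uses scores 16/122 = 13% on the first base and 16/16 = 100% on the second. The rule is therefore unclear as a payment rule. It covers log-in and all features, however, and Interventions lists testing locations and reminders among them, so PrEP entries alone do not measure it. No analysis in the document uses it.

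**Step 5: what depends on the count.** The only cut-off in the Statistical analysis plan is a SUS score above 50. App use has no pass mark, null value or comparator. The 122 above is a product of the assumptions, so a mean below it fails no criterion of the trial.

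**The case for a change.** The strongest case for a change is that these are primary feasibility outcomes, that regimen is open by design, and that the text permits a count which mixes regimen with engagement. Leaving the unit open also lets it be chosen after the data are seen. A few lines of SAP text would close this, and the follow-up questionnaire already covers PrEP use and sexual behaviour.

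Much of that stands. The denominator is missing, and a raw pooled count would be hard to interpret if regimens were mixed. Writing down the unit would be tidier.

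The step to a required change does not stand. The harm needs a pooled raw count that the plan never specifies. The obvious remedy, dividing diary entries by doses and episodes from the questionnaire, relies on recall over a month and on an instrument whose items are not in the document. Ratios could exceed 100%. It would also measure completeness of reporting, which is a different quantity from frequency of use. Splitting by regimen does not standardise sex reports, because episodes vary within a regimen, and subgroups of 31 to 70 men would be imprecise. This is a debatable trade-off with no clear gain.

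On the bonus, the limit is genuine: use is observed under payment, encouragement and monthly visits. But the plan draws no conclusion about unpaid uptake, so there is no claim to correct.

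**Conclusion.** No change to the plan is needed. This is missing detail that analysts would ordinarily fill: days with a log-in over days followed, diary counts shown with their unit and by regimen where regimen is recorded, and a note that use was observed under a bonus. The planned descriptive statistics and intervals would be accurate for the quantity they are labelled as, and no decision in the document depends on their level.

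The size of any distortion is unknown. Under the assumptions shown, the ratio between two perfect reporters runs from 1.0 to 7.6, and the distortion is nil if nearly all men dose daily. This conclusion rests on the outcomes staying descriptive, without a feasibility threshold or comparison group. If a target for component use were added, its denominator would have to be stated with it.

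### Does the diary–DBS correlation need a written rule for days without a diary entry?

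*Combined protocol and SAP*

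**What the plan says.** The Study design paragraph describes a single-group study "aiming to examine the preliminary effectiveness of the app in monitoring adherence to PrEP". The last paragraph of the Statistical analysis plan is the whole specification of the matching analysis. It calls for "comparing the pill-taking reports in the PrEP-taking diary component in the app with the Tenofovir (TDF) and Emtricitabine (FTC) drug concentration" in dried blood spots (DBS) "in the previous seven days before the follow-up day", using "correlation analysis to examine the consistency between the drug concentration in the DBS samples and self-reported PrEP diary in the app". The result is read simply: "Higher correlation reflects higher effectiveness of adherence monitoring". The type of correlation, the seven-day diary score and the handling of days without an entry are not stated, and no missing-data rule appears elsewhere.

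Three other places bear on blank days:
- **Interventions:** the app is meant to work whatever the user's "choice of dosing regimen and lifestyle".
- **Baseline visit:** "Participants will be encouraged to use all app components over the next four months". Daily entry is not required.
- **Incentives:** "Participants whose cumulative frequency of log-in and use of features reached 90% will receive an additional US" $33 bonus. This threshold concerns log-ins and features over the whole study, not diary days.

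The Statistical analysis plan also makes use of the app's components, including the pill-taking diary, a primary feasibility outcome with confidence intervals.

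**The concern.** The correlation is the only planned measure of how well the app monitors adherence, and its size is read directly as effectiveness. A blank day is ambiguous. For a daily user it may be a pill taken but not recorded; for someone on another regimen it may be a true day off. An analyst could score it as no pill, treat it as missing and use the proportion of entered days, or drop any week that is not fully entered. With no rule fixed, the choice could be made after the correlations are seen. A low r would also be hard to attribute: it could reflect pills not recorded or pills recorded falsely. Since use is only encouraged and the bonus is paid below 100%, some blank days are likely.

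**Working it through.** The plan gives no expected correlation, so there is no figure of its own to reproduce. The sample size (above 30, at most 70) rests on a rule of thumb and does not enter the argument.

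**1. Can the coding matter? (No assumptions.)** Take a week with four days recorded as taken and three blank.
- Blank = no pill: 4/7 = 57%.
- Blank = missing: 4/4 = 100%.
- Complete weeks only: the participant is dropped.

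So it can. With no blank days, all three codings agree.

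**2. How often would a window contain a blank?** Assumption: the 90% refers to diary days, and follow-up is about 120 days. A participant exactly at the threshold then has 0.10 × 120 = 12 blank days.
- Independent days: 1 − 0.9^7 = 0.52.
- One run of 12 days, averaged over all run and window positions: 0.15.

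At one DBS sample per participant, as Table 2 allows, that is about 5 to 16 of 31 windows, or 11 to 37 of 70. (The Follow-up visit text implies monthly drug measurement; the proportions are unaffected.) The bonus is not defined on diary days, so this only illustrates scale.

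**3. How far could r move?** Simulation of 400,000 windows, Pearson r. Assumed inputs:
- Daily pill probability is beta(2, 0.9), beta(8, 1), or a 50/50 mix of beta(8, 1) and beta(2, 4). Mean pill days are 4.8, 6.2 and 4.3 of 7.
- The DBS value is pill days plus normal noise, set so that r = 0.80 when every day is entered.
- Each person's completeness is beta(3c, 3(1 − c)), unrelated to pill-taking.

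| Mean completeness c | Blank = no pill | Entered days only | Complete windows | Windows kept |
|---|---|---|---|---|
| 0.9 | 0.70 / 0.51 / 0.74 | 0.78 / 0.76 / 0.79 | 0.80 | 66% |
| 0.7 | 0.54 / 0.31 / 0.62 | 0.72 / 0.67 / 0.75 | 0.80 | 26% |

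The complete-window value returns to 0.80 by construction, because entry was made independent of pill-taking.

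**4. What if entry depends on pill-taking?** Same mixed population, but the non-daily half leave every no-pill day blank. All entries are true.

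| c | Blank = no pill | Entered days only | Complete windows | Windows kept |
|---|---|---|---|---|
| 0.9 | 0.74 | −0.02 | 0.50 | 33% |
| 0.7 | 0.62 | 0.00 | 0.51 | 13% |

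About 99% of the complete windows come from daily users. Their pill counts vary little, so r falls through restriction of range and not through false entries. The plain count performs best here.

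**5. What would a restricted analysis cost in precision?** The 95% CI is tanh(atanh r ± 1.96/√(n − 3)). For r = 0.80:
- n = 31: 0.62 to 0.90.
- n = 70: 0.70 to 0.87.
- 26% of 31, about 8 windows: 0.22 to 0.96.

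**6. What does the plan's wording imply?** The quantity compared is pill-taking reports in a seven-day window. Counting reports gives zero for a day with none. That is the blank = no pill column, and a rule written to suit the aim would choose the same coding.

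**The case for a change.** The strongest reply is that the plan states neither a count nor a proportion, so an analyst could defend entered days only and obtain a visibly different r. In step 3 the two codings differ by 0.05 to 0.25 at 90% completeness. A separate simulation with Spearman correlation and other assumed inputs found median gaps between the highest and lowest of four codings of 0.07 to 0.39 at 90% entry. On this view one sentence in the plan would remove the freedom at no cost.

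The omission stands, and so does the fact that codings can disagree. Three parts do not carry the weight put on them.
- **Size.** The gaps depend entirely on assumed completeness and on how entry relates to pill-taking. The fall to zero requires non-daily users to leave every no-pill day blank. With entry only half as likely on those days, the separate simulation (n = 70, half non-daily, 90% entry otherwise) gives 0.70 for blank = no pill and 0.67 for entered days.
- **Expected gaps.** A bonus threshold below 100% for log-ins and features shows that incomplete use is tolerated. That diary days will be blank is an inference.
- **Attribution.** Diary use is reported separately as a feasibility outcome, and PrEP use is asked at each monthly visit. A reader can therefore set a low r beside how much was recorded, though not week by week.

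**Conclusion.** The concern does not call for a change. The plan leaves a rule unwritten, but its wording points to the sensible default: count recorded pills, with a blank contributing none. That coding keeps every window and matches the aim, because a pill the app failed to capture lowers its value as a monitor and ought to lower r. Following the plan as written gives the same main result as following an explicit rule.

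The alternatives offer no clear gain. Entered days only can collapse to r near zero when days off are left blank. Complete windows can give about 0.50 where full entry would give 0.80, with every entry true, so that figure could not be presented as the accuracy of entries. At 31 participants it may rest on a handful of windows.

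This rests on reading the diary score as a count. The sizes above are illustrations from assumed inputs, not forecasts. In a preliminary single-group study with no hypothesis test or correlation threshold, what remains is a missing detail that analysts can fill sensibly and state when they report r.

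### The diary–drug-level correlation takes no account of dosing regimen, so a higher pooled value need not mean better adherence monitoring

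*Combined protocol and SAP*

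**What the plan says.** The last paragraph of the Statistical analysis plan compares pill-taking reports in the app diary with tenofovir and emtricitabine levels in dried blood spots, over a window given as "in the previous seven days before the follow-up day". The method is one sentence: "We will use correlation analysis to examine the consistency between the drug concentration in the DBS samples and self-reported PrEP diary in the app". The reading rule is another: "Higher correlation reflects higher effectiveness of adherence monitoring". The plan names no type of coefficient, no threshold, and no split by or adjustment for regimen.

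The Interventions section describes the population: "The UPrEPU app is a self-monitoring tool to improve PrEP adherence regardless of the MSM user's choice of dosing regimen and lifestyle". The only inclusion criterion on PrEP use is "Currently taking PrEP or willing to initiate PrEP", so eligibility does not fix a regimen. The Sample size section gives "above 30 participants and 70 participants at maximum", justified by a central-limit-theorem rule of thumb. The baseline and follow-up questionnaires both ask about PrEP use.

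**The concern.** If regimens differ in pills per week, men on the higher-count regimen have both higher diary counts and higher drug levels. That gap alone makes the two measures rise together across the whole sample. It shows that the diary reflects which regimen a man follows, something the questionnaires on PrEP use could already supply. It does not show that the diary picks up pills taken or missed relative to a man's own regimen, which is what adherence monitoring means.

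The Study design section gives the aim as the app's preliminary effectiveness in monitoring adherence, and this correlation is the only quantitative analysis that addresses it. Under the SAP's reading rule, the conclusion could turn on which regimens happened to be enrolled.

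**Working it through.** **The plan's own figure.** There is none to reproduce. The documents state no expected or target correlation, and the sample size has no alpha, power or target r behind it.

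**Inputs.** From the documents: a seven-day window, regimen left to the user, and between 30 and 70 men. Assumed, because the documents are silent: two regimens, their mean pills per seven days, the share of men on each, the spread of drug levels, and one diary–sample pair per man. Table 2 fits one pair per man (follow-up 2, 3 or 4), but the Follow-up visit text measures concentration at every monthly visit. The two must be reconciled, because repeated pairs would need an analysis that allows for them.

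**Closed form.** Let p be the share on the second regimen, d the regimen gap in within-regimen SDs (taken as equal for diary and level), and r_w the within-regimen correlation. Then

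r_pooled = [r_w + p(1−p)d²] / [1 + p(1−p)d²].

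With r_w = 0, p = 0.3 and d = 2: p(1−p)d² = 0.21 × 4 = 0.84, so r = 0.84/1.84 = 0.46. With d = 1 it is 0.21/1.21 = 0.17; with d = 3 it is 1.89/2.89 = 0.65. If true tracking is r_w = 0.5, then at d = 2 pooling raises it to 1.34/1.84 = 0.73.

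**Model in pill counts.** True and diary counts are Binomial(7, mean/7). The level is the true count times a lognormal error with log-SD 0.3. A *useless* diary is drawn independently of the true count within regimen. A *perfect* diary equals the true count. Large simulated samples give:

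| Mean pills, higher vs lower regimen | Useless diary, pooled r at 10/30/50/70/90% of men on the higher regimen | Useless diary, adjusted r |
|---|---|---|
| 6 vs 2 | 0.45 / 0.64 / 0.66 / 0.61 / 0.40 | 0.00 |
| 6 vs 3 | 0.27 / 0.46 / 0.50 / 0.45 / 0.27 | 0.00 |
| 6 vs 4 | 0.13 / 0.26 / 0.30 / 0.27 / 0.15 | 0.00 |

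Hand check, 6 vs 2 at 50%:
- Between-regimen variance of the count: 0.25 × 4² = 4.
- Mean within-regimen variance: (0.857 + 1.429)/2 = 1.143, so diary variance = 5.143.
- Error moments: E[e] = exp(0.045) = 1.046 and E[e²] = exp(0.18) = 1.197.
- Level variance: (5.143 + 16) × 1.197 − 16 × 1.046² ≈ 7.81.
- Covariance: 4 × 1.046 = 4.18, so r = 4.18/√(5.143 × 7.81) = 0.66.

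**Comparison with a perfect diary, 6 vs 2.** Its pooled r is 0.88, 0.88, 0.85, 0.79 and 0.65 at the same five mixes. So a useless diary at a 50/50 mix (0.66) matches a perfect one at 90/10 (0.65).

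**At the planned sample sizes.** A second model used the log of the true count plus normal error (SD 0.3), a first regimen averaging 0.85 × 7 = 5.95 pills, and no within-regimen tracking.
- With 30% of men on the second regimen, median pooled r at n = 30 was 0.66, 0.49 and 0.30 when that regimen averaged 2, 3 and 4 pills. Nominal p < 0.05 occurred in 99%, 81% and 36% of runs.
- At n = 70 the medians were 0.64, 0.48 and 0.29, with p < 0.05 in 100%, 99% and 68%.
- In the weakest case (10% on the second regimen, 4 pills) the median was 0.17 at n = 30 and 0.16 at n = 70.
- The regimen-centred estimate was about 0 throughout, nominally significant in 5–8% of runs.

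**Precision.** The 95% limits are tanh(atanh(r) ± 1.96/√(n−3)). For r = 0.5 and n = 30: 0.549 ± 0.377, giving 0.17 to 0.73. For n = 70: 0.549 ± 0.239, giving 0.30 to 0.66. Adjusting for one two-level regimen replaces n−3 by n−4 and moves the lower limit at n = 30 to 0.16.

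**The case against.** Several objections have force.

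- **Pooling is inferred.** The SAP never says that regimens are combined. A reader might take it as stating a pooled analysis; it is only silent. Still, a single correlation with no regimen term, followed as written, pools the men.
- **The size is not known.** The documents name no regimens and give no mix. The entry requirement of at least four episodes of anal sex in the past month may narrow the pill gap. If nearly all men use one regimen, or the gap is small, the inflation is slight. This limits the size of the effect but does not remove it.
- **A useless diary is an extreme case.** Within a given mix the pooled value still ranks diaries correctly: at 6 vs 2 and 50%, perfect gives 0.85 and useless 0.66. Telling regimens apart is also some information about intake. This stands. The difficulty is that the mix is not fixed in advance and the plan gives no benchmark for r.
- **Adjustment has a distortion of its own.** Counts vary little in a near-daily regimen. A perfect diary gives only about 0.45 within the 6-pill group, and its adjusted r falls from 0.79 to 0.47 as that group goes from 10% to 90% of men (6 vs 2). So the adjusted value depends on the mix too and should not replace the pooled one as sole evidence. A single small regimen group says little: with 9 men, r = 0.5 has a 95% interval of −0.25 to 0.87.

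Two stronger inferences are not supported. One is that the plan leaves a hypothesis untested, namely that the app works for every regimen. The wording on regimen sits under Interventions and describes whom the app is for; it is not a stated hypothesis. The other is that men who have not started PrEP drive the correlation and should be left out. The documents give no number of such men, Table 2 places drug sampling at follow-up 2 to 4, and the calculations above include none.

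**Conclusion.** The point holds in a conditional form. The plan does not say how regimen enters the correlation, and the natural pooled coefficient cannot separate differences between regimens from tracking of taken and missed pills. With no within-regimen tracking and 10–90% of men on the higher-count regimen, the pooled value is about 0.40–0.66 (6 vs 2 pills per week), 0.27–0.50 (6 vs 3) or 0.13–0.30 (6 vs 4). These figures rest on assumed pill means, mix and error spread.

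The documents do not show that the trial's pooled result would be spurious, nor that an adjusted value would be free of dependence on the mix. They do show that the SAP's reading rule is unsafe without knowledge of regimen. The point is worth acting on because the change is cheap. It is not a fatal flaw: the study is a single-group one of preliminary effectiveness, its labelled primary outcomes are feasibility measures, and it sets no pass mark for r.

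**What to change.** Amend the last paragraph of the Statistical analysis plan to:

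1. Record, for each man, the regimen used in the seven days before the sample. The questionnaires on PrEP use are the obvious source.
2. Report the regimen-adjusted (partial) correlation with its 95% confidence interval beside the pooled correlation and its interval.
3. Add a scatter plot of diary count against drug level with points marked by regimen.
4. Qualify the reading rule: do not conclude that monitoring is effective from the pooled value alone.
5. State that a low adjusted value alone does not show that the diary fails, because restricted range within a near-daily regimen lowers r even for an accurate diary.

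The cost is SAP wording, one recorded variable and a little analysis, with no extra participants, visits or assays. The downside is that intervals will be wide at 30–70 men, and the adjusted value will probably look less favourable than the pooled one.
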